4.0 PATIENT ELIGIBILITY AND EXCLUSIONS

4.1 Inclusion Criteria

This protocol will have a 2 stage eligibility as consent will be done in the preoperative planning. Patients must meet all of the following criteria to be eligible for study entry.

Primary Eligibility (pre-op)

- Patients must be suspected of having a diagnosis of ovarian, fallopian tube or primary peritoneal cancer with a planned cytoreductive surgery.
- Borderline ovarian cancer with ascites.
- ECOG/Zubrod/SWOG Performance Status <2 (Karnofsky Performance Status \geq 70%)
- Female, age \geq 18 years
- Ability to provide informed consent
- Baseline laboratory values (bone marrow, renal, hepatic):
 - Adequate bone marrow function:

- Absolute neutrophil count >1000/ μ L
- Platelet count >100,000/ μ L
- Renal function:
 - Serum creatinine \leq 1.5 x ULN
- Hepatic function:
 - Bilirubin \leq 1.5x normal
 - Serum glutamic-oxaloacetic transaminase (SGOT) (aspartate aminotransferase [AST]) or serum glutamic-pyruvic transaminase (SGPT) (alanine aminotransferase [ALT]) levels \leq 2 x ULN
- No known bleeding disorders
- No known sensitivity to NSAIDs
- No active peptic ulcer disease
- No active bleeding

Secondary Eligibility

- Histologic diagnosis of epithelial ovarian, fallopian tube or primary peritoneal cancer on frozen section diagnosis
- Placement of an intraperitoneal port at the time of surgery for anticipated use for adjuvant chemotherapy or management of post-operative ascites
- If epidural catheter was used – the catheter must be removed prior to treatment
- No active bleeding

4.2 Exclusion Criteria

Patients meeting any of the following criteria are ineligible for study entry:

- Non-epithelial ovarian cancer or metastatic cancer to the ovaries
- Borderline ovarian cancer without ascites
- Presumed early stage ovarian cancer
- No clinical indication for a peritoneal port
- Active use of an epidural catheter
- Uncontrolled or unstable medical conditions
- Off study use of ketorolac or other NSAIDs prior to study administration
- Active bleeding or high risk of bleeding
- Active therapeutic anticoagulation
- Known hypersensitivity to NSAIDs
- Chronic or acute renal insufficiency as defined by a preoperative serum creatinine greater than 1.5mg/dL or creatinine clearance of < 60 ml/min
- Any co-morbid condition that, in the view of the attending physician, renders the patient at high risk from treatment complications

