1.5.3 Side Effects from Ketorolac

There are few side effects that are expected after a single dose. Side effects that are likely in 1% -10% chance include: pain at the IV site, rashes, itching, abdominal pain, gas, bleeding, mouth sores, constipation, diarrhea, bloating, heartburn, vomiting, upset stomach, ulcers, high liver function tests, low red cell count, swelling, increased bleeding time, purple spots, drowsiness, ringing in the ears, dizziness, sweating and abnormal kidney function. Side effects that have a greater than 10% chance of happening include: nausea and headaches. It is very unlikely that these side effects will occur from a single dose or even several doses over 24 hours. Many of these side effects will also be present just from the surgery and other medications given after the surgery.

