5.2 Study Population

Adult female subjects at least 18 years of age suspected of having a diagnosis of ovarian, fallopian tube or primary peritoneal cancer with a planned cytoreductive surgery will be eligible for this study.

Subjects will undergo a pre-operative and a post-operative eligibility evaluation. Subjects who meet all of the inclusion criteria and do not meet any of the exclusion criteria will be eligible for enrollment into the study.

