8.0 STUDY MODALITY

8.1 Ketorolac tromethamine (Toradol® Roche Pharmaceuticals)

Formulation: Ketorolac is supplied in sterile single use 1mL vials of 15 mg/mL (**NDC 55390-480-01**) and 30 mg/mL, 1 mL single-dose vials of 30mg/mL (**NDC 55390-481-01**). Supplies are obtained by the University Hospital (University of New Mexico) and stored in the Pyxis until ordered by the treating physician.

Preparation: Ketorolac tromethamine for IV use is supplied in 1 mL vials of either 15mg or 30mg individual dose which requires no reconstitution.

Storage: Vials of ketorolac tromethamine are stored at room temperature protected from light in the carton until use.

Dosing: Ketorolac tromethine will be dosed according to FDA approved recommendations. For planned **single dose (IV)** based on clinical scenario:

- Patients < 65 years of age: One dose of 30 mg.
- Patients ≥ 65 years of age, renally impaired and/or less than 50 kg (110 lbs) of body weight: One dose of 15 mg.

For planned **Multiple-Dose Treatment (IV)** for indicated pain management

- Patients < 65 years of age: The recommended dose is 30 mg ketorolac tromethamine injection every 6 hours. The maximum daily dose for these populations should not exceed 120 mg.

- For patients \geq 65 years of age, renal impaired patients, and patients less than 50 kg (110 lbs): The recommended dose is 15 mg ketorolac tromethamine injection every 6 hours. The maximum daily dose for these populations should not exceed 60 mg.

Adverse Effects: Complications of treatment with ketorolac tromethamine, such as G.I. ulceration, bleeding and perforation, postoperative bleeding, acute renal failure, anaphylactic and anaphylactoid reactions and liver failure have been described. These NSAID-related complications can be serious in certain patients for whom ketorolac tromethamine is indicated, especially when the drug is used inappropriately.

In patients taking ketorolac tromethamine or other NSAIDs in clinical trials, the most frequently reported adverse experiences and frequency are shown in the table below:

	< 1%	1%-10%	>10%
cardiovascular	CHF, palpitation, pallor, tachycardia, syncope	hypertension	
dermatologic	Alopecia, urticaria, photosensitivity	Injection site pain, rashes, pruritis	

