gastrointestinal	Anorexia, dry mouth, eructation, esophagitis, excessive thirst, gastritis, glossitis, hematemesis, hepatitis, increased appetite, jaundice, melena, rectal bleeding	Abdominal pain, flatulence, bleeding, perforation, stomatitis, constipation, diarrhea, GI fullness, heartburn, vomiting, dyspepsia, ulcers, elevated liver functions	nausea
heme and lymph	Ecchymosis, eosinophilia, epistaxis, leukopenia, thrombocytopenia	Anemia, edema, increased bleeding time, purpura	
metabolic/nutritional	Weight change		
nervous system	abnormal dreams, abnormal thinking, anxiety, asthenia, confusion, depression, euphoria, extrapyramidal symptoms, hallucinations, hyperkinesis, inability to concentrate, insomnia, nervousness,	Drowsiness, tinnitus, dizziness, sweating	headaches

	paresthesia, somnolence, stupor, tremors, vertigo, malaise		
reproductive	infertility		
respiratory	Asthma, cough, dyspnea, pulmonary edema, rhinitis		
urogenital	cystitis, dysuria, hematuria, increased urinary frequency, interstitial nephritis, oliguria/polyuria, proteinuria, renal failure, urinary retention	Abnormal renal function,	
others	Fevers, infections, sepsis, conjunctivitis		

Table 3. Reported toxicities of racemic ketorolac

Supplier: Manufactured by Bedford Laboratories™ Bedford, OH 44146 Div-KRL-P05. Vials are supplied directly to University Hospital.

Administration: Ketorolac 15mg or 30 mg doses will be administered via IV Push undiluted over 15 – 30 seconds. Prior to administration, the IV line will be flushed with 5-10 ml's NS. The ketorolac dose will be followed with a 5-10 ml NS push again to ensure the ketorolac completely clears the IV line.

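### Both serum creatinine limits apply before surgery, but ketorolac is given after it, and no renal check is required in between

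*Combined protocol and SAP*

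**What the plan says.** Eligibility has two stages. In 4.1, the creatinine limit (1.5 times the upper limit of normal) belongs to the pre-operative stage, under the item that begins "Baseline laboratory values (bone marrow, renal, hepatic". Section 4.2 excludes "Chronic or acute renal insufficiency as defined by a preoperative serum creatinine greater than 1.5mg/dL or creatinine clearance of < 60 ml/min". That wording covers acute as well as chronic insufficiency, yet dates the creatinine to before surgery.

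Secondary Eligibility in 4.1 lists four items: frozen-section histology, port placement, removal of any epidural catheter, and absence of active bleeding. Section 5.2 adds: "Subjects will undergo a pre-operative and a post-operative eligibility evaluation". It names no laboratory test for the second evaluation.

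Under 9.0, the study dose is given for post-operative pain. Section 8.1 lists for those "renally impaired and/or less than 50 kg (110 lbs) of body weight: One dose of 15 mg", without defining impairment. Section 9.0 gives 15 mg for mild renal insufficiency, with no cut-off and no time of measurement. Among the complications of the drug, 8.1 states: "postoperative bleeding, acute renal failure, anaphylactic and anaphylactoid reactions and liver failure have been described".

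**The concern.** The protocol treats renal function as a reason to withhold ketorolac and sets numbers for it. It then applies the creatinine numbers before major surgery, although exposure starts afterwards. Bleeding is handled differently: it is checked before surgery and again at Secondary Eligibility. Section 8.1 names acute renal failure alongside post-operative bleeding as a complication of the drug, but only bleeding is rechecked.

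What is at stake is the safety of individual patients. Someone who would have been excluded on a given creatinine before the operation can have that same value afterwards without meeting the stated creatinine exclusion. There is a lesser consequence for safety reporting. Section 13.2.1 asks for the suspected relationship of each adverse event to the drug, and without a creatinine taken after surgery and before the dose, a later rise is harder to attribute to either.

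**Working it through.** This is a check of timing, not of arithmetic. The plan states no figure to reproduce.

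1. **When each renal limit applies.** There are two serum creatinine limits. The one in 4.1 is placed in the pre-operative stage, and the one in 4.2 is worded as preoperative. Number that apply after surgery: 0 of 2.
2. **The clearance limit.** In 4.2 the word for the preoperative period clearly governs serum creatinine. It most naturally governs clearance too, but the grammar leaves room to read the 60 ml/min limit as undated. On that reading, the post-operative evaluation in 5.2 could apply it. No post-operative clearance is scheduled, however, and the serum creatinine limit is unaffected.
3. **What is rechecked after surgery.** Of the four Secondary Eligibility items, one concerns bleeding and none concerns renal function.
4. **Whether a value must exist at dosing.** Sections 10.1 and 10.3 require blood before the dose, but the assays described in section 10 do not include creatinine. Section 13.1 lists chemistry only as clinically specified. No post-operative creatinine is mandated before the dose.
5. **Whether the dosing text closes the gap.** Take an illustrative post-operative creatinine of 1.8 mg/dL (a reviewer's example, not a figure from the documents). Before surgery, 1.8 > 1.5, so 4.2 excludes the patient. After surgery, the creatinine limit in 4.2 is silent. The dose list in 8.1 gives 15 mg for renal impairment without an upper bound. Section 9.0 gives 15 mg for mild insufficiency only, which does set a bound, but an undefined one. Whether this patient is dosed depends on a physician's reading of that word.
6. **What else could stop the dose.** The following apply, and none carries a renal number:
   - in 4.2, the exclusions for unstable conditions and for high risk in the attending physician's view;
   - in 9.0, the condition that 30 mg goes to younger patients who are otherwise well, the requirement that repeat dosing is not contraindicated, and the reference to the package insert;
   - in 9.2, discontinuation for clinical worsening;
   - in 11.2.1, the expectation that ketorolac will have to be held back in some patients.

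Steps 1 to 4 establish the gap. Steps 5 and 6 show that it is covered only by judgement.

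**The case against.** The best answer is that renal checking has reasonably been left to clinical care. This is a pilot of an approved analgesic given for its own indication, with one study dose and any further doses at the physician's discretion. Section 1.5.3 calls the listed side effects very unlikely after one dose or several over 24 hours. The general exclusions can be applied at the post-operative evaluation, and 14.0 obliges the investigator to know the package insert. Section 13.2.2 provides an independent monitor who follows the first three patients continuously and can remove a subject. A physician who sees a clear rise in creatinine has ample authority to withhold the drug.

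Most of this stands, and it limits the weight of the point. It does not remove it. None of these provisions requires a creatinine to be available when the drug is given, and none carries the protocol's own limit forward to that time.

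A reader might go further and infer that the protocol itself expects surgery to disturb renal function, because 1.5.3 lists "sweating and abnormal kidney function" and then says "Many of these side effects will also be present just from the surgery and other medications given after the surgery". The documents do not support that. The list is long and mixed, and the sentence does not say that renal effects are among the many. The entry "Abnormal renal function" in the 1%-10% column of the toxicity table in 8.1 concerns patients taking the drug or other NSAIDs, not the effect of surgery.

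**Conclusion.** The gap is real. As written, a creatinine that first exceeds 1.5 mg/dL after surgery does not trigger the stated creatinine exclusion, and nothing requires that it be measured before the dose. This rests on the plain wording of 4.1 and 4.2. It holds for serum creatinine whichever way the clearance limit is read.

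Its size cannot be put as a probability, because the documents give no rate of new renal impairment after cytoreductive surgery. The point is a cheap improvement to patient safety, not a flaw that undermines the trial.

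Three stronger conclusions are tempting and should not be drawn:

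- **That patients with new impairment will be given ketorolac.** The judgement-based safeguards may well stop it.
- **That missed impairment doubles exposure under 6-hourly dosing.** Section 9.0 allows repeat doses only where they are not contraindicated, at the physician's discretion, and it reserves 30 mg for patients otherwise in good health.
- **That the primary endpoint is compromised because renal status sets the dose.** Section 11.2.1 pools the 15 mg and 30 mg groups in the expectation of similar drug measures, and the documents contain no concentrations in renal impairment from which an effect could be derived.

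**What to change.** - **4.1, Secondary Eligibility:** add a line requiring a post-operative serum creatinine not above 1.5 mg/dL and a creatinine clearance not below 60 ml/min, resulted before the study dose. The sample can be the predose draw already required in 10.1 and 10.3, or a clinical result from the same post-operative day.
- **4.2:** let the renal exclusion refer to preoperative or post-operative values.
- **8.1 and 9.0:** state that the 15 mg renal dose is decided on this result and applies only to patients within the 4.2 limits.

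The cost is a short amendment and one creatinine assay per patient. Ketorolac may have to wait for the result; 9.1 allows narcotics meanwhile. If the predose sample cannot be used and no second IV is in place, a needle draw may be needed. A few more patients may fail secondary eligibility. Section 11.2.1 already counts such failures among the 15-18 patients it expects to lose from 25, but the documents do not allow the addition to be estimated.

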5.0 STUDY DESIGN

5.1 Study Design

This is a pilot (feasibility) trial to determine the availability, concentration and racemic mixture of a clinically indicated pain medication, ketorolac, in the peritoneal cavity and the subsequent effect on free floating ovarian cancer cells in patients after cytoreductive surgery for ovarian cancer.

5.2 Study Population

Adult female subjects at least 18 years of age suspected of having a diagnosis of ovarian, fallopian tube or primary peritoneal cancer with a planned cytoreductive surgery will be eligible for this study.

Subjects will undergo a pre-operative and a post-operative eligibility evaluation. Subjects who meet all of the inclusion criteria and do not meet any of the exclusion criteria will be eligible for enrollment into the study.

6.0 SUBJECT INFORMATION AND CONSENT

The Investigator or her representative will explain the nature of the study to the subject, and answer all questions regarding this study. Prior to any study-related pre-operative and post-operative procedures being performed on the subject, the informed consent statement will be reviewed and signed and dated by the subject and the person who administered the informed consent. A copy of the informed consent form will be given to the subject and the original will be placed in the subject's medical record.

Spanish speaking subjects will be consented using a Spanish Short Form. A Certified Spanish Translator from the University of New Mexico will translate the study processes and procedures to the subject and family member.

The subjects will be re-consented if revisions are made to the consent form that would alter the subjects decision to participate in the trial.

7.0 STUDY RECRUITMENT PROCESS

The Principal Investigator, [name] and Co-Investigator, [name] will identify potential study participants through medical record review from patients within their practices. The Investigators will discuss this study with subjects during the subjects pre-operative counseling visit.

Subjects will not be compensated for participation in the research study.

8.0 STUDY MODALITY

8.1 Ketorolac tromethamine (Toradol® Roche Pharmaceuticals)

Formulation: Ketorolac is supplied in sterile single use 1mL vials of 15 mg/mL (**NDC 55390-480-01**) and 30 mg/mL, 1 mL single-dose vials of 30mg/mL (**NDC 55390-481-01**). Supplies are obtained by the University Hospital (University of New Mexico) and stored in the Pyxis until ordered by the treating physician.

Preparation: Ketorolac tromethamine for IV use is supplied in 1 mL vials of either 15mg or 30mg individual dose which requires no reconstitution.

Storage: Vials of ketorolac tromethamine are stored at room temperature protected from light in the carton until use.

Dosing: Ketorolac tromethine will be dosed according to FDA approved recommendations. For planned **single dose (IV)** based on clinical scenario:

- Patients < 65 years of age: One dose of 30 mg.
- Patients ≥ 65 years of age, renally impaired and/or less than 50 kg (110 lbs) of body weight: One dose of 15 mg.

For planned **Multiple-Dose Treatment (IV)** for indicated pain management

- Patients < 65 years of age: The recommended dose is 30 mg ketorolac tromethamine injection every 6 hours. The maximum daily dose for these populations should not exceed 120 mg.

- For patients \geq 65 years of age, renal impaired patients, and patients less than 50 kg (110 lbs): The recommended dose is 15 mg ketorolac tromethamine injection every 6 hours. The maximum daily dose for these populations should not exceed 60 mg.

Adverse Effects: Complications of treatment with ketorolac tromethamine, such as G.I. ulceration, bleeding and perforation, postoperative bleeding, acute renal failure, anaphylactic and anaphylactoid reactions and liver failure have been described. These NSAID-related complications can be serious in certain patients for whom ketorolac tromethamine is indicated, especially when the drug is used inappropriately.

In patients taking ketorolac tromethamine or other NSAIDs in clinical trials, the most frequently reported adverse experiences and frequency are shown in the table below:

	< 1%	1%-10%	>10%
cardiovascular	CHF, palpitation, pallor, tachycardia, syncope	hypertension	
dermatologic	Alopecia, urticaria, photosensitivity	Injection site pain, rashes, pruritis	
gastrointestinal	Anorexia, dry mouth, eructation, esophagitis, excessive thirst, gastritis, glossitis, hematemesis, hepatitis, increased appetite, jaundice, melena, rectal bleeding	Abdominal pain, flatulence, bleeding, perforation, stomatitis, constipation, diarrhea, GI fullness, heartburn, vomiting, dyspepsia, ulcers, elevated liver functions	nausea
heme and lymph	Ecchymosis, eosinophilia, epistaxis, leukopenia, thrombocytopenia	Anemia, edema, increased bleeding time, purpura	
metabolic/nutritional	Weight change		
nervous system	abnormal dreams, abnormal thinking, anxiety, asthenia, confusion, depression, euphoria, extrapyramidal symptoms, hallucinations, hyperkinesis, inability to concentrate, insomnia, nervousness,	Drowsiness, tinnitus, dizziness, sweating	headaches

	paresthesia, somnolence, stupor, tremors, vertigo, malaise		
reproductive	infertility		
respiratory	Asthma, cough, dyspnea, pulmonary edema, rhinitis		
urogenital	cystitis, dysuria, hematuria, increased urinary frequency, interstitial nephritis, oliguria/polyuria, proteinuria, renal failure, urinary retention	Abnormal renal function,	
others	Fevers, infections, sepsis, conjunctivitis		

Table 3. Reported toxicities of racemic ketorolac

Supplier: Manufactured by Bedford Laboratories™ Bedford, OH 44146 Div-KRL-P05. Vials are supplied directly to University Hospital.

Administration: Ketorolac 15mg or 30 mg doses will be administered via IV Push undiluted over 15 – 30 seconds. Prior to administration, the IV line will be flushed with 5-10 ml's NS. The ketorolac dose will be followed with a 5-10 ml NS push again to ensure the ketorolac completely clears the IV line.

9.0 TREATMENT PLAN

All patients will receive a single dose of IV ketorolac for pain management for the indication of post-operative pain control. The single dose will be considered the study dose for which all consenting eligible patients will receive. The dose of IV ketorolac will be determined per the recommendations in the package insert. Patients less than 65 years of age and in otherwise good health will receive a 30mg IV single dose. Patients 65 years of age or greater, or who have mild renal insufficiency or are of low weight (as per section 3.2) will receive a single 15 mg dose IV ketorolac. In patients who have a clinical pain response and have no contraindications to multi-dose (every 6 hours over 24 hours), additional doses will be given per physician discretion based on clinical indication. Patients receiving 24 hour dosing will be eligible for sample time points after 24 hour dosing.

9.1 Concomitant and Excluded Therapies

Use of other non-steroidal (NSAIDs) medications during the time-points of this trial is not permitted while participating in this study. Narcotic regimens with or without acetaminophen is allowed. If patients require additional NSAIDs for pain control, the patients will be withdrawn from study although data collected prior to withdrawal will be included in the analysis. Use of cytotoxic chemotherapy during this trial is not allowed, however if the clinical situation warrants immediate chemotherapy, the patient will be withdrawn from the trial. Prophylactic anticoagulation is allowed but therapeutic anticoagulation is a direct exclusion criteria.

Use of concurrent investigational agents is not permitted.

